## 2.3.2 KNOWN POTENTIAL BENEFITS

The information collected from this study will further our knowledge of secondary brain injury after TBI. Also, we will assess whether sildenafil therapy alters blood flow, which is hypothesized to be protective after TBI. Even though this study does not offer direct benefit to participants, the data collected will help shape how TBIs are managed in the future. The MR images will be collected for research purposes only. If any abnormalities are observed we will contact the medical monitors. The benefits outweigh the risks associated with this study.

#### **3 OBJECTIVES AND PURPOSE**

The main objective of this clinical trial is to test the hypothesis that sildenafil treatment in active professional boxers/MMA fighteres soon after concussion normalizes CBF, potentiates CVR, reduces symptoms, improves cognition, and is a tolerable therapy. If our hypothesis is supported, sildenafil will shape how secondary brain injury is treated and will improve long-term outcomes after TBI.

## 4 STUDY DESIGN AND ENDPOINTS

#### 4.1 DESCRIPTION OF THE STUDY DESIGN

In this placebo-controlled, double-blinded clinical trial, approximately 100 boxers/MMA fighters that have experienced a concussion or a significant number of sub-concussive blows will be treated with a placebo pill or Viagra® (sildenafil; 60mg) once (single-dose therapy) or once-a-day for 14 days. This is a phase 2 study that will be conducted at a single-site (UTSWMC, Dallas, Texas).

Prior to competition, the medical/concussion history and a blood (8ml) and saliva sample will be collected at the baseline (pre-fight) visit. Also, a battery of neuropsychological exams (NIH Common Data Elements) and a magnetic resonance imaging (MRI) scan will be performed at UT Southwestern Medical Center Advanced Imaging Research Center to obtain cognitive, structural, and functional baseline data.

At day1-3 and 30 after injury, the boxers will undergo the MRI structural and MRI BOLD (with hypercapnia) procedures at UT Southwestern Medical Center Advanced Imaging Resource Center. The subjects will also undergo neurpsychological testing, and blood/saliva collection for tests to determine the efficacy of sildenafil. A randomization schedule will be prepared by the study statistician. Randomization will be 1:1 sildenafil:placebo, and will be in blocks of 2. Investigators associated with this study will not have access to the randomization schedule. The principal investigator, study team, and study subjects will be blinded in this study. To monitor the drug administration, a daily diary will be filled out by the participant. The tolerability of sildenafil in boxers will also be assessed.

A total of 130 boxers will be screened and only 100 boxers will be enrolled in this study to complete the study aims. The study participants will not be responsible for any research related costs, which include travel and parking when visiting UTSWMC for the collection of blood/saliva, neuropsychological testing, and MR imaging. The participants will be compensated for their time.

The participants in **group 1** (single therapy) will consist of the active boxers/MMA fighters that experience significant sub-concussive blows or a concussion during competition. In this group, 65, professional male/female boxers/MMA fighters within the North Texas region will be screened and about 50 concussed athletes will be enrolled. The athletes that have at least 25 blows to the head and a Symptom Score > 1 on at least 3 items from the Rivermead Post-Concussion Questionnaire following their fight will be enrolled in this study. The research subjects will be treated with sildenafil (60mg), once at 2 hours after experiencing a concussion.

**Group 2** will consist of the active boxers/MMA fighters that experience significant subconcussive blows or a concussion during competition. In this group, 65, professional male/female boxers/MMA fighters within the North Texas region will be screened and about 50 concussed athletes will be enrolled. The athletes that have at least 25 blows to the head and a Symptom Score > 1 on at least 3 items from the Rivermead Post-Concussion Questionnaire following their fight will be enrolled in this study. Once enrolled, the subjects will be treated with sildenafil (60mg) once-a-day for 14 days.

**Healthy Control group:** In this study, 80, age (between 18 and 35)-matched healthy controls will be enrolled. The control subjects will participate in neuropsychological testing, blood/saliva collection, and the MR imaging procedures. Healthy controls will be tested in group 1 (n=40) and 2 (n=40) and randomized to receive either sildenafil or placebo in this group.

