	matter degeneration (3-13). Recently, use of magnetic resonance imaging (MRI)-Blood Oxygen Level Dependent (BOLD) combined with hypercapnia (high spatial and temporal resolution) by our research group has proven to be more sensitive at measuring alterations of cerebral blood flow (CBF) in TBI subjects. The goal of our proposed research is to test the efficacy of Viagra® (sildenafil) at normalizing CBF and improving cognitive outcomes in people that have experienced a TBI. Sildenafil is a phosphodiesterase-5 (PDE- 5) inhibitor that has previously been administered as a therapy for high blood pressure and erectile dysfunction (14, 15). In people that have been affected by stroke-induce neurotrauma, sildenafil improved CBF and was found to be neuroprotective (16-21). With respect to chronic TBI, our preliminary data demonstrates that sildenafil therapy potentiates cardiovascular reactivity (CVR) in areas of the brain with damaged endothelium. In this proposal, we will test the hypothesis that sildenafil treatment in boxers/MMA fighters soon after concussion normalizes CBF, potentiates CVR, reduces post-concussion symptoms, and improves cognition.
Objectives:	
 
Objective 1: To demonstrate that administration of the vasodilator, sildenafil, to concussed boxers/MMA fighters will improve/normalize various vascular properties.
 
Objective 2: We will determine if sildenafil reduces symptoms and improves cognition in the athletes.
 

Endpoint	The primary outcome measures will be global CVR to hypercapnia, reduced symptoms, improved cognition in concussed athletes treated with a single or multiple doses of sildenafil (60mg). In the secondary outcome measure, we assess sildenafil (60mg) therapy reduces the levels of fluid-based biomarkers of injury.
Population:	The study population for this protocol consists of 100 boxers between the ages of 18 and 35 (both men and women) who have suffered a concussion. The athletes will be recruited from fitness centers within the North Texas area. Testing will occur at UT Southwestern Medical Center, Dallas, Texas. The study will be comprised of the experimental (boxers/MMA fighters) and age- matched non-boxer, healthy controls.
Phase:	2
Number of Sites enrolling participants:	1

STU032018-063, [name], FormA-ResearchProtocol, Mod\_6, 11-25-19 (1) NIH-FDA Clinical Trial Protocol

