## 5 STUDY ENROLLMENT AND WITHDRAWAL

## 5.1 PARTICIPANT INCLUSION CRITERIA

## FOR ATHLETES

- 1. Age 18-35
- 2. Male or female professional boxers/MMA fighters
- 3. Ability to undergo MR imaging procedures
- 4. At least one of the following:
  - a. KO/TKO scored by fight referee.
  - b. Greater than 25 blows to the head.
- Significant post-concussive symptoms (Symptom Score > 1 on at least 3 items from the Rivermead Post-Concussion Questionnaire)
   FOR CONTROLS
- 1. Age 18-35
- 2. Male of female who do not participate in contact sports
- 3. Screen negative for mTBI using Ohio State TBI ID

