#### **Statistical analyses**

Preliminary analyses: Prior to the formal analyses, we will conduct exploratory data analysis by examining the distributions of the key variables using descriptive statistics and graphic tools. In particular, baseline variables (demographics, concussion history and injury severity characteristics) will be examined to determine whether outliers are present. The baseline characteristics of the 100 enrolled boxers/MMA fighters will be compared with 80 controls using linear regression and two sample testing. Continuous variables (primary and secondary outcomes) will be summarized through standard measures of central tendency and spread including means, medians, standard deviations and IQRs. Frequency distributions will be calculated for categorical variables (CBF/CVR, post-concussion symptoms,

neuropsychological measurements). Data transformations will be used if needed to produce variables that conform to the distributional assumptions underlying the analytic techniques. Both primary and secondary outcomes will be evaluated under the intent-to-treat principle, meaning that all available data on all randomized participants, regardless of adherence to the study protocol, will be included and analyzed according to the treatment assignment, although compliance will be closely monitored via pill counting. Statistical analysis will be performed with SAS (SAS Institute, Cary, NC, USA) and R software.

Primary analyses: Our primary analysis (**Aim 1**) will be driven by the primary hypothesis that administration of single or multiple doses of sildenafil will improve CBF/CVR, lower symptoms and improve cognition. Boxplots of CBF and CVR of concussed boxers after sildenafil and placebo periods will first be plotted and compared with values at Day 1-3 and 30 post-TBI as well as with the 80 controls.

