Also, we will assess the treatment effect of sildenafil on post-concussive symptoms and cognitive performance using two-sample t-test similarly as in the primary aim, but with the secondary endpoints of symptoms. On day 1 and 30 after injury we will then calculate the difference in CBF/CVR and each of the post-concussive symptom assessments and cognitive assessments after the single treatment of sildenafil. Also, we will assess the post-concussion correlations of CBF/CVR and cognitive performance by calculating the cross-sectional Pearson correlations of CBF/CVR with symptom inventory and neuropsychological CDEs collected at Day 1 and 30 after TBI. Correlations will be calculated separately and jointly at each time point, and for each of the subdomains of neuropsychological CDEs. Multiple comparisons will be adjusted by controlling the false discovery rate (FDR).

Our secondary analyses will consist of assessing the treatment effect of sildenafil therapy on brain biomarker levels using two-sample t testing, but with the secondary endpoints of symptoms. We will then calculate the difference in brain biomarker levels at the beginning of the sildenafil therapy and after the treatment period (Day 30 vs Day 1-3). Scatter plots including both arms will be generated based on the calculated differences and two linear regression models with changes in brain biomarkers as outcomes, and changes in symptoms as independent variables will be fit to assess the association between the recovery of the TBI-related markers. Potential confounders such as gender and treatment arm indicator will be adjusted in the model.

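### Controls are called age-matched with no procedure beyond the shared 18-35 range, and sex is neither matched nor adjusted, so reading fighters' CBF or CVR as abnormal or normalized against them is open to confounding

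*Combined protocol and SAP*

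**What the plan says.** **Who the controls are.** The protocol summary (Population) describes age-"matched non-boxer, healthy controls". Section 4.1, under the healthy control group, puts it this way: "In this study, 80, age (between 18 and 35)-matched healthy controls will be enrolled". That bracketed range is the only detail given on matching.

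**Eligibility (5.1).** Athletes and controls both need to be 18-35. On sex, the athlete criterion reads "Male or female professional boxers/MMA fighters" and the control criterion reads "Male of female who do not participate in contact sports". Controls must also screen negative for mTBI. No sex ratio, quota, age band or pairing rule is given for either group.

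**Analysis (10.1, Statistical analyses).** Two athlete-control comparisons are written:
- Preliminary analyses: "The baseline characteristics of the 100 enrolled boxers/MMA fighters will be compared with 80 controls using linear regression and two sample testing".
- Primary analyses: boxplots of CBF and CVR, "compared with values at Day 1-3 and 30 post-TBI as well as with the 80 controls".

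Neither names a covariate. In the secondary analyses, for the regressions of biomarker change on symptom change, the plan says: "Potential confounders such as gender and treatment arm indicator will be adjusted in the model". Age is not named as a covariate anywhere.

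**What the controls are for.** Objective 1 in the summary and the main objective in section 3 both speak of normalizing vascular properties or CBF.

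**The concern.** A common entry range is an eligibility limit. It does not align two age distributions: athletes averaging 30 and controls averaging 21 would both satisfy it. Sex has no safeguard, since both groups take men and women and nothing ties the control mix to that of professional fighters. The plan recognises gender as a potential confounder, but adjusts for it in a model of associations between outcome changes and not where athletes are set beside controls, two groups that were not randomized against each other.

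What is at stake is the word normalize. The athletes' pre-fight scan is a within-person reference for the current bout, but it comes from professional fighters whose concussion history is taken at that same visit, and section 2.1 reports lower CBF and CVR in people with a history of TBI. Only the controls are screened negative for mTBI, so only they can show whether fighters start out abnormal or end up in a normal range. A different sex or age mix could create that difference or hide it, and enrolling more controls would not remove it.

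**Working it through.** The plan states no sample size, power or effect size for athletes against controls, so there is no figure to reproduce. The check has a textual part and an illustration of size.

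**1. Textual check.**

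| Place | Age | Sex |
|---|---|---|
| Summary, Population | called matched, no method | not mentioned for controls |
| 4.1, control group | matched, with 18-35 in brackets | not mentioned |
| 5.1, both groups | 18-35 for each | either sex, no quota |
| 10.1, preliminary and primary comparisons with controls | no covariate | no covariate |
| 10.1, biomarker-symptom models | not named | gender adjusted |

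**2. Sex: size on assumed inputs.** The documents give neither a sex mix nor a sex effect. Assume that the male share differs by 20-40 percentage points between groups and that the outcome differs between men and women by 0.3-0.8 SD.

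Bias = (difference in male share) x (sex effect in SD)
- Low end: 0.2 x 0.3 = 0.06 SD
- High end: 0.4 x 0.8 = 0.32 SD

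**3. Standard error of the unadjusted difference, in SD units.**
- Baseline, all participants: sqrt(1/100 + 1/80) = sqrt(0.0225) = 0.15.
- After treatment: 4.1 also randomizes the controls to sildenafil or placebo, so a clean comparison uses placebo recipients only. At 1:1, with both dosing groups pooled, that is about 50 v 40: sqrt(1/50 + 1/40) = sqrt(0.045) = 0.21.

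The bias is therefore 0.06/0.15 = 0.4 to 0.32/0.15 = 2.1 standard errors at baseline, and 0.06/0.21 = 0.3 to 0.32/0.21 = 1.5 standard errors in the placebo-only comparison.

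**4. Age: size on assumed inputs.** A mean age gap of 2-6 years with a slope of 0.01-0.05 SD per year gives 2 x 0.01 = 0.02 to 6 x 0.05 = 0.30 SD.

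**5. Does adjustment work, and what does it cost?** One simulated scenario (4,000 runs, 100 v 80) had no true athlete-control difference. Inputs, all assumed: 10% women among athletes and 50% among controls, sex effect 0.5 SD, mean ages 27 and 24 (SD 4, held within 18-35), age slope 0.03 SD per year. The expected false difference is 0.4 x 0.5 + 3 x 0.03 = 0.20 + 0.09 = 0.29 SD.
- Unadjusted: mean false difference 0.29 SD, standard error 0.154.
- Adjusted for sex and age: mean difference 0.00, standard error 0.178, an increase of 0.178/0.154 - 1 = 16%.

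**The case against.** The strongest reply is that this leaves the trial's main inference untouched, and that is right. Sildenafil against placebo is randomized 1:1, so the composition of the control group cannot bias that contrast. Section 2.2 gives the pre-fight baseline as the reason for choosing this population, and change from it is within person. A reader might infer that the treatment effect is compromised, or that controls are the only uninjured reference. The documents support neither.

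Second, a reader might infer an inflated false-positive rate. That presumes an unadjusted athlete-control test of CBF or CVR, which is not clearly planned. The tested comparison is of baseline characteristics, and the same paragraph lists baseline variables as demographics, concussion history and injury severity. The CBF/CVR comparison is a boxplot with no p-value. The concern is thus about a biased difference and how it is read. Demographics compared between groups would also make an imbalance visible, although choosing covariates after seeing it is weaker than naming them beforehand.

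Third, a reader might extend the point to cognition. Controls take the neuropsychological tests (4.1, 7.1.1), but no athlete-control cognition test is written.

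Fourth, it can be said that 4.1 means a range plus real matching, and that naming linear regression leaves room for covariates. Both readings are possible, but no matching procedure and no covariate is written, so someone following the plan would have neither.

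What remains is narrower than a threat to the primary result, but it is real: the comparison with the mTBI-negative reference group is unprotected against sex and age differences.

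**Conclusion.** The point holds for the athlete-control reading only. The plan labels the controls age-matched without a procedure beyond the shared range. It neither matches nor adjusts for sex in the comparisons with controls, and it does not name age as a covariate anywhere. A claim that fighters' CBF or CVR is abnormal, or has been normalized, relative to controls could reflect composition.

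The size cannot be computed from the documents. The 0.06-0.32 SD range rests wholly on the assumed sex imbalance and sex effect, and the age range likewise on assumed inputs. If sex mix and mean age happen to agree, the bias is negligible, but the plan does nothing to make them agree. This is worth correcting before analysis because the remedy is simple, but it is no reason to doubt the randomized comparison.

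**What to change.** - **10.1:** Make any athlete-control comparison of CBF, CVR or another outcome a linear model with sex and age as pre-specified covariates. Leave the comparison of demographics itself unadjusted, since its purpose is to show imbalance. Show the boxplots by sex, or add adjusted means.
- **10.1:** For comparisons after treatment, state which treatment arms of athletes and controls are being compared, because both are randomized.
- **4.1 and 5.1:** Recruit controls to track the athletes' sex mix and broad age distribution, and say how. Otherwise delete the age-matched label here and in the summary, and rely on the covariates.
- **7.3.2:** Confirm that sex is recorded. The baseline visit lists demographic information without itemising it. Age is already an entry criterion, and 10.1 already uses gender in a model, so new data collection should not be needed.

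Cost: a somewhat larger standard error if the groups are imbalanced (0.154 to 0.178 in the illustration) and, if controls are recruited to match, control enrolment that must follow athlete accrual.

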## 4.2 STUDY ENDPOINTS

## 4.2.1 PRIMARY ENDPOINT:

To determine if sildenafil administration improves CBF/CVR, reduces symptoms, and improves cognitive performance in concussed boxers/MMA fighters. Hypothesis: Both single and multiple sildenafil therapy improves CBF/CVR, symptoms, and cognition in concussed boxers. Also, long-term administration of daily doses of sildenafil to concussed boxers/MMA fighters is well tolerated. Following injury, we will enroll 100, active boxers/MMA fighters and 80, controls into a double-blind, placebo-controlled study. At a 1:1 ratio, the subjects will receive a single treatment of either placebo or sildenafil. The purpose of this study is to determine if sildenafil treatment improves CBF/CVR, reduces symptoms, and improves cognitive outcomes. In this study we will treat the injured athletes once (within 2 hours of injury) or daily (for 14 days) to determine if sildenafil improves outcomes. Previous clinical studies conducted by our research group, we found that sildenafil treatment (60mg) is tolerable within the TBI population. The athletes will maintain a daily diary of symptoms. At day 1-3 and 30 after injury, the CBF/CVR MR imaging procedures, the Rivermead Post Concussion Symptom Questionnaire, and neuropsychological assessments (NIH Common Data Elements) will be conducted to study the effect of sildenafil therapy. Blood (8cc) and saliva will also be collected to measure brain biomarkers of injury. Tolerability (blood testing and symptom reporting) assessments will be conducted throughout the study to ensure that the symptomatic boxers tolerate multiple, daily doses of sildenafil.

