# 6.1.5 DOSING AND ADMINISTRATION

STU032018-063, [name], FormA-ResearchProtocol, Mod\_6, 11-25-19 (1) NIH-FDA Clinical Trial Protocol

In the first and second group, the participants will be administered either a single-dose or 14 pills of placebo or sildenafil (60mg) after suffering a concussion. The first dose will be taken at 2hours after injury.

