## 10 STATISTICAL CONSIDERATIONS

#### 10.1 STATISTICAL AND ANALYTICAL PLANS

#### STATISTICAL ANALYSIS PLAN

#### Study design and randomization scheme

Once eligibility is confirmed, based upon defined inclusion and exclusion criteria, randomization will occur within 2 hours of a bout. The placebo-controlled double-blind design will diminish concern about predictability of treatment assignments. The unblinded study biostatistician will prepare a randomization schedule. Randomization will be 1:1 sildenafil:placebo, and will be in blocks of 2. Treatment allocation will be determined via a computer program that automatically generates random digits. Investigators associated with this study will not have access to the randomization schedule. The randomization program will also record the assignments to the corresponding boxers in the database and will display the assignments on the screen for action by the study coordinators.

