#### Drug Treatment and Randomization:

We will enroll 100 concussed boxers/MMA fighters using a double-blind, placebocontrolled design. The athletes will be randomized at a 1:1 ratio to either placebo or sildenafil for single or multiple doses (once-a-day for 14 days).

A randomization schedule will be prepared by the study statistician. Investigators associated with this study will not have access to the schedule. The PI, study team, and participants will be blinded.

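### Two sections conflict on what the 80 healthy controls receive, and their randomisation, first dose and Day 1-3 and Day 30 assessments have no stated starting point

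*Combined protocol and SAP*

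**What the plan says.** All references are to the combined protocol and SAP.

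- **Section 4.1, Healthy Control group:** "Healthy controls will be tested in group 1 (n=40) and 2 (n=40) and randomized to receive either sildenafil or placebo in this group". The same section defines group 1 as a single dose and group 2 as once-daily dosing for 14 days.
- **Section 4.2.1:** "Following injury, we will enroll 100, active boxers/MMA fighters and 80, controls into a double-blind, placebo-controlled study". The next sentence reads "At a 1:1 ratio, the subjects will receive a single treatment of either placebo or sildenafil". Further on, the choice between one dose and 14 days is described for the injured athletes only.
- **Sections that describe treatment without mentioning controls:** the opening of 4.1 names those treated as "approximately 100 boxers/MMA fighters that have experienced a concussion", or with many sub-concussive blows. Section 10.2.1 says "The athletes will be randomized at a 1:1 ratio to either placebo or sildenafil for single or multiple doses". Section 10.1 has the randomisation program record assignments against boxers.
- **Section 7.1.1, procedures table:** the lead-in links treatment to athletes and speaks only of procedures for controls. The table itself is headed for both populations and has rows for randomisation and for dispensing study drug.
- **Timing:** section 10.1 says "randomization will occur within 2 hours of a bout", and section 6.1.5 says "The first dose will be taken at 2hours after injury". Under section 5.1, controls take no part in contact sports and must have a negative mTBI screen.
- **Section 10.1, primary analyses:** athletes' CBF and CVR are to be plotted against the 80 controls, treated as a single group.

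**The concern.** The protocol should let staff say, for any healthy volunteer, whether that person takes study drug, for how many days, and on which day the scans fall. Here two sections give different regimens, and the sections that carry out randomisation and dosing are written around a fight. A coordinator cannot randomise a control relative to a bout, or give a first pill relative to an injury, when there was neither.

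Two things are at stake. One is the drug exposure of healthy people, which should not depend on the section consulted. The other is the meaning of the athlete-versus-control comparison. If controls are randomised as section 4.1 says, the 80 are not a drug-free reference group but a mixture of sildenafil and placebo under two regimens, and the analysis section does not separate them.

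**Working it through.** **1. Inputs.** 80 controls, 40 per group (4.1); 100 athletes (4.1, 4.2.1); single dose or 14 daily doses (4.1); allocation 1:1 (4.1, 4.2.1). The control paragraph of 4.1 gives no ratio of its own, so applying the trial-wide 1:1 to controls is an assumption.

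**2. The plan's own figure.** 40 + 40 = 80, which agrees with the stated total. Controls are 80 / (100 + 80) = 44% of participants.

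**3. Active doses to controls under each statement.**

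| Statement | Single-dose sildenafil | 14-day sildenafil | Active doses |
|---|---|---|---|
| 4.1, Healthy Control group | 40/2 = 20 | 40/2 = 20 | 20x1 + 20x14 = 300 |
| 4.2.1, read literally | 80/2 = 40 | 0 | 40x1 = 40 |

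Both statements put 40 controls on sildenafil. They differ in whether 20 of them take 14 doses or one: 20 x (14 - 1) = 260 = 300 - 40.

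**4. What the times are counted from.**

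| Event | Section | Counted from | Usable for controls? |
|---|---|---|---|
| Randomisation | 10.1 | bout | No |
| First dose | 6.1.5 | injury | No |
| Dosing visit (Visit 2) | 7.3.2 | injury | No |
| Day 1-3 and Day 30 assessments | 4.1, 4.2.1, 4.2.2, 7.2.1, 7.2.3 | injury | No |
| Group 2 daily dosing | 4.1 (written for athletes) | enrolment | Could be |
| Telephone contacts | 8.3 | enrolment | Yes |
| Early-termination MRI rule | 7.3.3 | enrolment | Yes |
| Visit 5 | 7.3.2 | completion of the study | Yes |
| Procedures-table columns; Visit 3 and 4 headings | 7.1.1, 7.3.2 | not named | Unclear |

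The first four rows cover randomisation, the first pill and the endpoint measurements. No section gives controls a substitute for the bout or the injury. The procedures table places randomisation and dispensing under Day 1-3 without saying what the days follow.

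**5. Make-up of the comparison group.** Under 4.1 at 1:1, the 80 controls are 20 single-dose sildenafil, 20 single-dose placebo, 20 on 14-day sildenafil and 20 on 14-day placebo. So 40/80 = 50% are allocated to active drug. The analysis section names no control arms.

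**The case against.** The strongest reply is that only the control paragraph of section 4.1 deals specifically with control treatment, and it is explicit. The single-treatment sentence in 4.2.1 covers athletes and controls alike, so it contradicts the athletes' 14-day group just as much and looks like a slip. The header and rows of the procedures table agree with 4.1. This stands as an account of what was probably meant. It does not remove the conflict in a dosing statement, and it supplies no timing rule for controls.

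Three stronger readings are tempting and are not supported:

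- **Controls get no drug.** A reader might infer this because 10.1, 10.2.1 and the opening of 4.1 speak only of athletes or boxers. That is silence, not exclusion. No section says controls are untreated, 6.1.5 speaks of participants, and the procedures table includes controls alongside its randomisation and dispensing rows. A third plan with zero doses cannot be read out of the text.
- **Every dosing and visit time depends on an injury.** The second table shows otherwise. The baseline visit in 7.3.2 also carries a Day 0 label, but nothing says that controls' later visits are counted from it.
- **The trial's main comparison is undermined.** The sildenafil-placebo comparison among athletes does not use the controls. The comparison of baseline characteristics precedes dosing and is also unaffected.

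The effect on the control comparison has limits too. The planned display is descriptive and does not say which control visit is used; pre-dose values would not be mixed by treatment. Section 2.1 cites studies finding no effect of sildenafil on CBF in healthy people, although the analysis section does not rely on this and also compares CVR. On safety, the exclusions in 5.2 are not restricted to athletes, and the adverse-effect row of the procedures table covers controls. Finally, the design schematic and consent pages are not in the text available here and might bear on the question.

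**Conclusion.** The concern holds in a limited form. Sections 4.1 and 4.2.1 contradict each other on the controls' regimen: 300 active doses to healthy volunteers against 40, assuming 1:1 allocation and a literal reading of 4.2.1, which may be a drafting slip. Separately, and whichever regimen is meant, the stated rules for randomisation, first dose and the dosing visit cannot be applied to controls, and their Day 1-3 and Day 30 assessments have no stated origin. Under 4.1, about half of the control group in the CBF/CVR comparison would be allocated to sildenafil, so any post-dose comparison with the pooled 80 has no clear meaning. All 80 controls (44% of 180) are affected. This is more than missing detail and should be corrected, but it leaves the randomised athlete comparison intact.

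**What to change.** Reconcile sections 4.1, 4.2.1, 6.1.5, 7.1.1 (lead-in and table), 7.3.2 (Visit 2), 10.1 and 10.2.1 so that they make one statement on:

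1. whether controls are randomised to study drug and, if so, to which regimen and in what ratio; and
2. what their randomisation, first dose and visit days are counted from.

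Name controls explicitly in each of these places. The regimen and the anchor are for the sponsor to decide; this review takes no position on either.

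Then align the control comparison in 10.1 with that statement. State which control visit is used and, if controls are randomised, do not pool their post-dose values across sildenafil and placebo.

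The cost is a wording amendment to these sections and the procedures table, with the IRB review that section 13.2 requires of any amendment. It adds no participants or procedures.
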